### **2-3 Sample Size Calculation**

The sample size was calculated using the standard formula for cross-sectional studies, with the following parameters: a 95% confidence level, a 5% margin of error, and an expected prevalence of psychological distress of 50% to yield the largest possible sample size. Based on these assumptions, the minimum required sample size was estimated to be 384 participants. To enhance the statistical power and compensate for potential non-response or incomplete data, a larger sample was targeted. Consequently, a total of 500 breast cancer patients were enrolled in the final analysis, exceeding the minimum requirement.

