## **2-6 Data Analysis**

Data was analyzed using IBM SPSS Statistics version 26. Descriptive statistics (mean, standard deviation, frequency, and percentage) were used to summarize demographic and clinical variables. The Kolmogorov-Smirnov test was applied to assess the normality of continuous variables, and due to non-normal distribution, non-parametric tests were used.

Bivariate analyses included Spearman's correlation coefficient to evaluate associations between psychological outcomes (depression, anxiety, stress) and continuous predictors such as sleep quality, cost, and number of children. The Kruskal-Wallis H test was employed to examine differences in distress levels across cancer stages.

Categorical associations were evaluated using Pearson's Chi-square test. Binary logistic regression analysis was conducted to identify predictors of severe anxiety. Additionally, multivariate linear regression models were constructed for each psychological outcome (PHQ-9, GAD-7, stress), and multicollinearity was assessed using the Variance Inflation Factor(VIF).

Receiver Operating Characteristic (ROC) curve analysis was used to assess the predictive accuracy of stress scores for severe anxiety, with Area Under the Curve (AUC) interpreted based on conventional thresholds. Conceptual path modeling was used to explore potential indirect relationships between stress and anxiety, mediated by sleep disturbance and impaired daily performance.

All tests were two-tailed, and a p-value of less than 0.05 was considered statistically significant.

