**Table 2.** Spearman Correlation Matrix Among Study Variables

Variable	PHQ9_Total	GAD7_Total	Stress Level	Sleep Difficulty	Sleep Satisfaction	Total Cost

PHQ9_Total	1.00	0.79	0.66	0.85	0.49	-0.11
GAD7_Total	0.79	1.00	0.65	0.77	0.62	-0.10
Stress Level	0.66	0.65	1.00	0.85	0.55	-0.12
Sleep Difficulty	0.85	0.77	0.85	1.00	0.48	-0.08
Sleep Satisfaction	0.49	0.62	0.55	0.48	1.00	-0.09
Total Cost	-0.11	-0.10	-0.12	-0.08	-0.09	1.00

[figure not shown]
Spearman correlation coefficients between psychological outcomes and sleep-related variables are shown in **Table 2**. Strong positive correlations were observed between depression, anxiety, stress, and sleep difficulty.

**Table 3.** Kruskal–Wallis Test for Differences Across Cancer Stages

Variable	Chi-square (H)	df	P-value
Stress Level	31.092	3	<0.001
PHQ9_Total	14.762	3	0.002
GAD7_Total	19.705	3	<0.001

The Kruskal–Wallis test results (**Table 3**) indicate significant differences in depression, anxiety, and stress levels across cancer stages ( $P < 0.05$ ).

**Figure 1.** Chi-square (H) Values for Stress, Depression, and Anxiety

**Figure 1** shows the Chi-square (H) values for stress, depression, and anxiety. Stress exhibited the highest value (H = 31.09), followed by anxiety (H = 19.71) and depression (H = 14.76), all indicating significant differences across groups ( $P < 0.05$ ).

**Table 4.** Multiple Regression Analysis of Factors Associated with Depression, Anxiety, and Stress among Patients

Outcome	Predictor	B	T	P-value	VIF	R 
Depression (PHQ-9)	Use of Sedatives	4.842	10.817	<0.001	1.766	0.702
	Sleep Difficulty	4.52	11.221	<0.001	4.866	
	Sleep Satisfaction	0.364	2.01	0.045	1.021	
	Children	0.075	0.626	0.532	1.039	
	Total Cost	7.5E-5	2.209	0.028	1.022	

	Metastatic	-0.13	-0.408	0.684	1.048	
Anxiety (GAD7)	Use of Sedatives	4.064	12.807	<0.001	1.766	0.615
	Sleep-related Worry	1.521	6.193	<0.001	3.655	
	Sleep Satisfaction	0.539	1.886	0.060	4.866	
	Children	0.205	1.889	0.060	1.039	
	Total Cost	3.0E-5	1.246	0.213	1.022	
	Metastatic	0.203	0.896	0.371	1.048	
Stress Level	Use of Sedatives	1.856	29.413	<0.001	1.766	—
	Sleep-related Worry	0.149	3.048	0.002	3.655	
	Children	0.037	1.705	0.089	1.039	
	Metastatic	0.084	1.865	0.063	1.048	
	Total Cost	3.4E-6	0.711	0.477	1.022	

The results of the multiple regression analysis are summarized in **Table 4**. Use of sedatives and sleep-related worry were significant predictors of stress, depression, and anxiety scores.

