#### 4- Discussion

The present study provides a comprehensive psychosocial profile of breast cancer patients in Al-Anbar, Iraq, highlighting significant associations between psychological distress, sleep disturbance, disease stage, economic burden, and emotional regulation. The results of our study reveal that depression and anxiety levels were remarkably high among breast cancer patients, with strong correlations to sleep-related variables and the use of sedative medications. These findings are consistent with previous studies from Iraq and neighboring countries, which emphasize the underrecognized psychological morbidity among cancer patients (13).

Specifically, the elevated stress levels observed in our study appear closely tied to poor sleep quality and increased reliance on sedatives. This pattern is consistent with findings from Iranian oncology research, where 66.8% of cancer patients reported poor sleep quality (PSQI > 5), strongly associated with symptoms of anxiety and depression (14)

Similarly, (14) Demonstrated that more than one-third of cancer patients experienced subjective sleep disturbances, with 6.1% relying on sedative medication. These findings highlight disrupted sleep as a key contributor to psychological distress in oncological care and support the growing understanding that impaired sleep quality may serve as a potential clinical indicator of emotional dysregulation in cancer care.

However, other studies have reported conflicting results. For example, (15) found that while sleep disturbances were prevalent among cancer patients, they were not consistently associated with heightened anxiety or depression. Such discrepancies may be explained by differences in patient populations, cancer types, cultural factors, and methodological variations across studies.

The results of the current study revealed that advanced cancer stage was significantly associated with increased levels of psychological distress, particularly anxiety and depression. After adjusting for stage coding, regression models confirmed that advanced cancer stage predicted elevated anxiety scores ( $\beta = 0.92$ ,  $p = 0.001$ ), which aligns with previous findings from oncology populations in the region(16). This association may reflect the psychological impact of disease severity, poor prognosis, increased treatment burden, and concerns about disease progression and its potential complications.

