## 6-Conclusion

This study highlights the multifactorial nature of psychological distress among breast cancer patients in Al-Anbar, Iraq. Depression, anxiety, and stress were significantly linked to sleep disruption, sedative use, disease stage, and emotional dysregulation. Advanced cancer stage emerged as a key predictor of heightened anxiety and depression. These findings emphasize the need to integrate psychosocial assessment and targeted interventions into oncological care, particularly in low-resource settings, to mitigate psychological morbidity and improve quality of life in this population.

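### The Conclusion names advanced stage as a predictor of depression and anxiety, but no adjusted model of depression contains stage, and its adjusted association with severe anxiety reverses between Tables 5 and 6

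*Combined protocol and SAP*

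**What the plan says.** Table 1 lists two separate variables: Cancer Stage, ranging from 0 to 4, and Metastatic, coded 0/1 with mean 0.36.

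Section 2-6 Data Analysis plans one analysis by stage: "The Kruskal-Wallis H test was employed to examine differences in distress levels across cancer stages". It also plans a linear model for each of PHQ-9, GAD-7 and stress and a logistic model for severe anxiety. It lists no covariates for any of them and does not mention metastatic status.

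In section 3 the variables are used as follows:

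- **Table 3** (unadjusted): stage, for stress, PHQ-9 and GAD-7.
- **Table 4** (adjusted linear models): Metastatic only, with no stage row. The depression row reads "Metastatic -0.13 -0.408 0.684 1.048" and the anxiety row "Metastatic 0.203 0.896 0.371 1.048" (B, T, p, VIF). The stress row has B = 0.084, T = 1.865, p = 0.063.
- **Tables 5 and 6** (logistic models of severe anxiety): stage only.

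The Discussion says that "advanced cancer stage was significantly associated with increased levels of psychological distress, particularly anxiety and depression". It later uses the stage differences to argue for interventions tailored to stage. The Conclusion goes further: "Advanced cancer stage emerged as a key predictor of heightened anxiety and depression".

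**The concern.** Calling stage a predictor of depression suggests that it kept an association in a model with other factors. No such model of depression is printed. The one adjusted estimate of disease extent for depression is for a different variable, lies close to zero, and is not discussed.

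The Results text makes this hard to notice. Its list of significant predictors from linear regression includes stage with a coefficient of 0.92 and p = 0.0014. Those are the Table 6 figures, from a logistic model of severe anxiety. The Discussion then repeats 0.92 as evidence that stage predicts higher anxiety scores. A reader would reasonably think that a linear model with a stage term exists.

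At stake is one of the study's main conclusions, and the argument for stage-specific support that is built on it.

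**Working it through.** **1. Stage and depression.** Table 3 gives H = 14.762 on 3 df. The upper chi-square tail is 0.0020, as printed. For GAD-7, H = 19.705 gives 0.0002, consistent with the printed p < 0.001. As a measure of size, H/(N - 1) is 14.762/499 = 0.030 for PHQ-9 and 19.705/499 = 0.039 for GAD-7. The test is an omnibus one and carries no direction. The Results say distress was higher in advanced disease, but no scores by stage are shown. The 3 df imply four groups, whereas the Table 1 range of 0 to 4 allows five codes, so the grouping also needs stating.

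**2. Metastatic in Table 4.** Inputs are the printed B and T, N = 500, and the number of predictors in each model (6, 6 and 5), which gives 493, 493 and 494 residual df. SE = B/T and 95% CI = B ± 1.965 × SE. The two-sided p-values from T are 0.683, 0.371 and 0.063, against 0.684, 0.371 and 0.063 printed.

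- PHQ-9: SE = 0.13/0.408 = 0.319; CI -0.76 to 0.50. Divided by the Table 1 SD of 6.11, this is -0.12 to 0.08 SD.
- GAD-7: SE = 0.203/0.896 = 0.227; CI -0.24 to 0.65. Divided by 3.81, this is -0.06 to 0.17 SD.
- Stress: SE = 0.084/1.865 = 0.045; CI -0.004 to 0.172. The upper limit divided by 0.79 is 0.22 SD.

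As a cross-check, SE should be close to SDy × √[(1 - R²) × VIF/df]/SDx. For PHQ-9, 6.11 × √(0.298 × 1.048/493)/0.48 = 0.320. For GAD-7, 3.81 × √(0.385 × 1.048/493)/0.48 = 0.227. Both agree with the values from B/T, so the rows are internally consistent.

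**3. Stage and severe anxiety.** Table 5 gives an odds ratio of 0.61 (0.33 to 0.87), a log odds of ln 0.61 = -0.49, and the text calls advanced stage protective. Table 6, labelled a corrected model, gives a coefficient of 0.92 (0.36 to 1.48). The odds ratio is exp(0.92) = 2.51, with limits exp(0.36) = 1.43 and exp(1.48) = 4.39. Its z of 3.20 gives p = 0.0014, as printed. The direction therefore reverses. The text under Table 5 says that Table 6 confirmed the Table 5 associations, which is not so for stage. The only explanation offered is a brief reference in the Discussion to an adjustment of stage coding. Table 5 also includes stress level, which Table 6 does not.

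**4. Where the text mentions Metastatic.** It appears as a row in Tables 1 and 4. The sentence under Table 4 names only sedative use and sleep-related worry. The rest of the Results text, the Discussion and the Conclusion do not report its estimates.

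**The case against.** Four points can be made for the study team.

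- **The variables are not interchangeable.** If Metastatic means distant disease (the documents do not define it), stage III patients fall in its reference group. A gradient across the non-metastatic stages could exist alongside a null Metastatic term. This stands.
- **The analyses differ in more than the disease variable.** For depression, Table 3 is unadjusted, while Table 4 adjusts for sedative use and for sleep difficulty, which correlates 0.85 with PHQ-9 in Table 2. For anxiety, Table 6 models a binary outcome adjusted for PHQ-9, anger and psychological support, while Table 4 models the continuous score with other covariates. A reader might infer that two definitions of one exposure gave contradictory answers. The documents do not support that, because variable, outcome scale and adjustment set change together.
- **Sleep and sedative use may lie on the pathway from disease extent to distress.** The study itself treats sleep as a mediator between stress and anxiety. A conditional null then does not refute an unadjusted association. This also stands. The stress interval, which is almost wholly positive, is not a demonstrated null even on those terms.
- **Nothing was withheld.** A reader might infer that results were reported selectively. Every Metastatic row is printed with B, T and p. The number of children, also non-significant in all three models, goes equally undiscussed, and the Methods name stage rather than metastatic status. Stage was not uniformly the favourable choice either, given Table 5. Selection is not shown.

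None of this supplies an adjusted stage result for depression, or explains the reversal between Tables 5 and 6.

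**Conclusion.** The point holds as one about what the Conclusion can claim. For depression, the stage statement rests on a single unadjusted omnibus test with H/(N - 1) of about 0.03. The adjusted linear models contain only Metastatic, whose 95% intervals reach no higher than about 0.08 SD for PHQ-9 and 0.17 SD for GAD-7, and the text does not mention it. For anxiety, adjusted stage evidence exists only for severe anxiety, with odds ratios of 0.61 and about 2.5 in two models of the same outcome.

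A reader might go further and take Table 4 to show that disease extent is unrelated to distress. It does not: the estimates are conditional on sedative use and sleep, and Metastatic is not stage. What stage would show in those models cannot be computed from the documents.

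The intervals assume that the printed rows are all the predictors in each model, that all 500 patients contribute, and that code 1 means metastatic.

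**What to change.** 1. Refit the three Table 4 models with Cancer Stage, coded as in Tables 3 and 6, and state that coding. Keep the Metastatic models as a second analysis.
2. Report the Metastatic estimates with 95% CIs in the Results and Discussion. Name the adjustment set, because refitted stage terms would carry the same conditional meaning.
3. In the Results, move the 0.92 from the linear-regression list to the logistic model it comes from, and correct the matching Discussion sentence. Explain the reversal between Tables 5 and 6.
4. Until the refits support more, limit the Conclusion to three statements. Depression differed across stages in an unadjusted test. Metastatic status was not associated with depression or anxiety scores after adjustment for sedative use and sleep. The association of higher stage with severe anxiety comes from the Table 6 model and is reversed in Table 5.

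The cost is three refits on existing data, some rewriting and a less emphatic Conclusion. No new data are needed.
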